## **Week 3**

1. Check to see if any information on participant's contact sheet needs to be updated.
2. Administer the CO test. Refer to the CO directions under the "CO Monitor" section on **Page 8** of this manual. Record the CO level in REDCap.
  - If the CO level is 3 or below, you need to administer a urine cotinine test to confirm that the participant is using nicotine products.
3. Collect the participant's Tobacco Use and NRT Use calendars and enter the data for the previous week into the appropriate SPSS database, then return the calendars to the participant.
4. Collect the used nicotine patches and inhaler cartridges and dispose of them after reviewing the calendars. Any unused patches/inhaler cartridges can be given back to the participant.
5. Gather either the 21 mg patch or the 14 mg patch and give it to the participant. **(Patch dosage is based on number of cigarettes smoked determined at Baseline appointment). Be sure to write down the time that the patch is placed on their arm. Ideally, the participant should have the patch on for 30 minutes before the intervention begins.**
6. Gather the nasal spray bottle and give it to the participant to use. **Wait to give the nasal spray to the participant until the session is being recorded.**
7. Have the participant fill out all of the questionnaires related to the session in REDCap, **except the SECOND Minnesota Nicotine Withdrawal Scale and the SECOND Questionnaire of Smoking Urges.**
8. While the participant is filling out the questionnaires on REDCap, have REDCap open on the desktop and double check for participant entry errors as they progress through the questionnaires.
9. Tell the client that you are about to start the recording for the session. Explain that "this is a manualized intervention; therefore it will not feel like traditional therapy. We will be working from a manual and will adhere to the manual content, exclusively."
10. Turn on the recording and **state your name, the date, and the time that you are starting the therapy. Do your best not to say the participant's name while being recorded.**
11. Tell the participant to follow along in their client Intervention workbook as you go through your Therapist Intervention Manual
12. When appropriate, pause the audio recording and have the participant fill out the following:
  - **The second Minnesota Nicotine Withdrawal Scale**
  - **The second Questionnaire of Smoking Urges**
    - **Based on the participant's response to the Minnesota Nicotine Withdrawal Scale and the Questionnaire of Smoking Urges, graph the before and after scores in their workbook.**
13. Un-pause the audio recording and continue the intervention by going over the participant's before and after scores for the Minnesota Nicotine Withdrawal Scale and Questionnaire of Smoking Urges.
14. Go over the Tobacco Use and NRT Use calendars.

15. Provide them with the copies of the calendars (in their folder) to keep in their pocket/wallet for use when they do not have their manual with them.
16. After the therapy, ask the participant if they have any questions. If they do not, tell them you are ending the recording.
17. Schedule the next appointment for the following week (preferably the same day of the week and the same morning time). **Once you have it scheduled, make sure the appointment is placed in the [name] Lab Google Calendar.**
18. Instruct the participant to **bring the calendars and workbook back so they can be reviewed next session.**
19. Give the participant 6 patches. The 6 patches and the patch they are currently wearing (total of 7) will last through to the next appointment.
20. Give the participant one bottle of nasal spray. The nasal spray bottle will last through to the next appointment. **Be sure to emphasize they are not to use the nasal spray on the morning of the next appointment.**
21. Have the participant sign for the medication in the medication sign-out log.
22. Mark in the Medication Inventory Excel sheet how many of the patches and nasal spray bottles you have given out so that we maintain a running total of prescriptions we have on hand.
23. Remind the participant of the instructions on how to use the patches and nasal spray and let them know they can reference their workbook if they forget. Give the participant the instructions sheet.
24. Compensate the participant on their Greenphire ClinCard.
25. Give the participant an appointment card. **Be sure to remind the participant to try and refrain from smoking the night before the appointment and not to use a patch or nasal spray on the morning of the appointment. Also, remind them to bring all used and unused patches, patch packets, and nasal spray bottles back to the next appointment.**
26. Upload the session recording to Box.com (MOP, pg. 14) and complete the Audio Recording Length form in REDCap.

## **Week 4**

1. Check to see if any information on participant's contact sheet needs to be updated.
2. Administer the CO test. Refer to the CO directions under the "CO Monitor" section on **Page 8** of this manual. Record the CO level in REDCap.
  - If the CO level is 3 or below, you need to administer a urine cotinine test to confirm that the participant is using nicotine products.
3. Collect the participant's Tobacco Use and NRT Use Calendars and enter the data for the previous week into the appropriate SPSS database, then return the calendars to the participant.
4. Collect the used nicotine patches and nasal spray bottles and dispose of them after reviewing the calendars. Any unused patches/nasal spray bottles can be given back to the participant.
5. Gather either the 21 mg patch or the 14 mg patch and give it to the participant. **(Patch dosage is based on number of cigarettes smoked determined at Baseline appointment). Be sure to write down the time that the patch is placed on their arm.**

**Ideally, the participant should have the patch on for 30 minutes before the intervention begins.**

6. Gather the 4mg or 2mg nicotine lozenge and give it to the participant to use. **(Lozenge dosage is based on how soon participant smokes their first cigarette after waking, as reported at Baseline appointment). Wait to give the lozenge to the participant until the session is being recorded.**
7. Have the participant fill out all of the questionnaires related to the session in REDCap, **except the SECOND Minnesota Nicotine Withdrawal Scale and the SECOND Questionnaire of Smoking Urges.**
8. While the participant is filling out the questionnaires on REDCap, have REDCap open on the desktop and double check for participant entry errors as they progress through the questionnaires.
9. Tell the client that you are about to start the recording for the session. Explain that “this is a manualized intervention; therefore it will not feel like traditional therapy. We will be working from a manual and will adhere to the manual content, exclusively.”
10. Turn on the recording and **state your name, the date, and the time that you are starting the therapy. Do your best not to say the participant’s name while being recorded.**
11. Tell the participant to follow along in their client Intervention workbook as you go through your Therapist Intervention Manual. Let them know that the counseling could take up to 30 minutes and **they are urged to write down information in their workbooks.**
12. When appropriate, pause the audio recording and have the participant fill out the following:
  - **The second Minnesota Nicotine Withdrawal Scale**
  - **The second Questionnaire of Smoking Urges**
    - **Based on the participant’s response to the Minnesota Nicotine Withdrawal Scale and the Questionnaire of Smoking Urges, graph the before and after scores in their workbook.**
13. Un-pause the audio recording and continue the intervention by going over the participant’s before and after scores for the Minnesota Nicotine Withdrawal Scale and Questionnaire of Smoking Urges.
14. Go over the Tobacco Use and NRT Use calendars.
15. Provide them with the copies of the calendars (in their folder) to keep in their pocket/wallet for use when they do not have their manual with them.
16. After the therapy, ask the participant if they have any questions. If they do not, tell them you are ending the recording.
17. Schedule the next appointment for the following week (preferably the same day of the week and the same morning time). **Once you have it scheduled, make sure the appointment is placed in the [name] Lab Google Calendar.**
18. Instruct the participant to **bring the calendars and workbook back so they can be reviewed next session.**
19. Give the participant 6 patches. The 6 patches and the patch they are currently wearing (total of 7) will last through to the next appointment.
20. Give the participant one box of lozenges (3 quit tubes = 72 lozenges). The 72 lozenges should last through to the next appointment if the participant uses 10 daily as advised. **Be**

**sure to emphasize they are not to use the lozenges on the morning of the next appointment.**

21. Have the participant sign for the medication in the medication sign-out log.
22. Mark in the Medication Inventory binder how many of the patches and quit tubes you have given out so that we maintain a running total of prescriptions we have on hand.
23. Remind the participant of the instructions on how to use the patches and lozenges and let them know they can reference their workbook if they forget. Give the participant the instructions sheet.
24. Compensate the participant on their Greenphire ClinCard.
25. Give the participant an appointment card. **Be sure to remind the participant to try and refrain from smoking the night before the appointment and not to use a patch or lozenges on the morning of the appointment. Also, remind them to bring all used and unused patches, patch packets, and lozenge quit tubes back to the next appointment.**
26. Upload the session recording to Box.com (MOP, pg. 14) and complete the Audio Recording Length form in REDCap.

## **Week 5**

1. Check to see if any information on participant's contact sheet needs to be updated.
2. Administer the CO test. Refer to the CO directions under the "CO Monitor" section on **Page 8** of this manual. Record the CO level in REDCap.
  - If the CO level is 3 or below, you need to administer a urine cotinine test to confirm that the participant is using nicotine products.
3. Collect the participant's Tobacco Use and NRT Use calendars and enter the data for the previous week into the appropriate SPSS database, then return the calendars to the participant.
4. Collect the used nicotine patches and lozenge quit tubes and dispose of them after reviewing the calendars. Any unused patches/lozenges can be given back to the participant.
5. Gather either the 21 mg patch or the 14 mg patch and give it to the participant. **(Patch dosage is based on number of cigarettes smoked determined at Baseline appointment). Be sure to write down the time that the patch is placed on their arm. Ideally, the participant should have the patch on for 30 minutes before the intervention begins.**
6. Have the participant fill out all of the questionnaires related to the session in REDCap, **except the Alliance Questionnaire, SECOND Minnesota Nicotine Withdrawal Scale and the SECOND Questionnaire of Smoking Urges.**
7. While the participant is filling out the questionnaires on REDCap, have REDCap open on the desktop and double check for participant entry errors as they progress through the questionnaires.
8. Tell the client that you are about to start the recording for the session. Explain that "this is a manualized intervention; therefore it will not feel like traditional therapy. We will be working from a manual and will adhere to the manual content, exclusively."

9. Turn on the recording and state your name, the date, and the time that you are starting the therapy. Do your best not to say the participant's name while being recorded.
10. Tell the participant to follow along in their client Intervention workbook as you go through your Therapist Intervention Manual. Let them know that the counseling could take up to 30 minutes and they are urged to write down information in their workbooks.
11. When appropriate, pause the audio recording and have the participant fill out the following:
  - **The Alliance Questionnaire**
  - **The second Minnesota Nicotine Withdrawal Scale**
  - **The second Questionnaire of Smoking Urges**
    - Based on the participant's response to the Minnesota Nicotine Withdrawal Scale and the Questionnaire of Smoking Urges, graph the before and after scores in their workbook.
12. Un-pause the audio recording and continue the intervention by going over the participant's before and after scores for the Minnesota Nicotine Withdrawal Scale and Questionnaire of Smoking Urges.
13. Review each week and the participant's experience with the short-acting forms of NRT from the participant's manual. Answer any questions the participant has regarding the medications. Present the medication selection sheet, review it with the participant, and explain that they will be selecting their preferred short-acting NRT to use in conjunction with the patch for the rest of the medication period of the study. Once the participant has made a selection, enter it into REDCap and ask them to write it in their manual.
14. After the therapy, ask the participant if they have any questions. If they do not, tell them you are ending the recording.
15. Schedule the next appointment for the next week (preferably the same day of the week and the same morning time). This appointment should be scheduled with another study staff member other than the therapist who saw the participant for the five weekly sessions. Once you have it scheduled, make sure the appointment is placed in the [name] Lab Google Calendar.
16. Give the participant 6 patches. The 6 patches and the patch they are currently wearing (total of 7) will last through to the next appointment.
17. Give the participant enough of the short-acting NRT they chose to last through to the next appointment.
18. Have the participant sign for the medication in the medication sign-out log.
19. Mark in the Medication Inventory Excel sheet how many of the patches and gum packages/lozenge quit tubes/inhaler cartridges/nasal spray bottles you have given out so that we maintain a running total of prescriptions we have on hand.
20. Remind the participant of the instructions on how to use the patches and gum/lozenges/inhaler/nasal spray and let them know they can reference their workbook if they forget.
21. Give the participant a study phone and charger and instruct them to complete the EMA's daily.
22. Compensate the participant on their Greenphire ClinCard.

23. Give the participant an appointment card. Also, remind them to bring all used and unused patches, patch packets, and short-acting NRT back to the next appointment.
24. Upload the session recording toBox.com (MOP, pg. 14) and complete the Audio Recording Length form in REDCap.

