### **Survey Queue:**

The survey queue is a way for participants to fill out questionnaires in REDCap in a more user-friendly display. When in survey mode, the screen simply shows the questionnaire with a submit button at the bottom. Once begun, the questionnaires will automatically load in the appropriate order corresponding to whichever session or visit the participant is attending. If a subject accidentally forgets to answer something, the survey prevents them from moving on, which gives staff the opportunity to assist if necessary. It is very important to note that surveys must be completed in the order they are shown.

To access the survey queue:

- Follow the steps as above, titled “Entering New Participant Data” or “Adding to Existing Participant Data”, depending on whether you are working with a new or existing subject
- From the **Record Home Page**, select the **CO Level** Data Collection Instrument, corresponding to the appropriate appointment, e.g. Baseline, Week 1, etc.
- Toward the upper right corner of the form, there is a gray drop down box titled **“Survey Options.”** Click this box and select **“Open Survey.”** A new tab will open displaying the form now in survey display. If the tab does not open, try clicking **“Open Survey”** again or double-clicking.
- Staff should fill out **CO Level**, select **“Submit”**, and the next form will auto load. The survey queue is set up to stop before loading the questionnaires for participants. The screen will indicate you have finished with that set of surveys, and will provide a link at the bottom to start the next set to be filled out by the participant.

- When appropriate, select that link and have the participant proceed through the queue. The queue will automatically stop again before loading any other questionnaires intended to be filled out after the counseling session or completed by staff, for example.

\*\*You can access the survey queue from any of the measures set up as surveys by again selecting “**Open Survey**” from the gray “**Survey Queue**” drop down box toward the upper right corner of the page.

\*\*Surveys display on the **Record Home Page** as complete with a green circle and white check mark.

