**Participants should work with the same staff member for the 5 weekly counseling sessions.**

#### Intervention Group A

##### Week 1

1. Check to see if any information on participant's contact sheet needs to be updated.
2. Administer the CO test. Refer to the CO directions under the "CO Monitor" section on Page 8 of this manual. Record the CO level in REDCap.
  - If the CO level is 3 or below, you need to administer a urine cotinine test to confirm that the participant is using nicotine products.
3. Gather either the 21 mg patch or the 14 mg patch and give it to the participant. **Patch dosage is based on number of cigarettes smoked determined at Baseline appointment. Be sure to write down the time that the patch is placed on their arm. Ideally, the participant should have the patch on for 30 minutes before the intervention begins.**
4. Gather either the 4mg gum or 2mg gum and give it to the participant. **Gum mg is based on how soon the participant smokes a cigarette after waking determined at Baseline**

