- **Wisconsin Inventory of Smoking Dependence Motives:** Subject fills out form within REDCap Survey Queue. Verify form is completed before allowing participant to leave. **Completed at Baseline, Week 5, Week 6, Week 9, Week 13, and Month 1 Follow-up.**

- **Attitudes About Nicotine Replacement Therapy:** Subject fills out form within REDCap Survey Queue. Verify form is completed before allowing participant to leave. Completed at all visits.
- **Abstinence-Related Motivational Engagement (ARME):** Subject fills out form within REDCap Survey Queue. Verify form is completed before allowing participant to leave. Completed at all visits.
- **Smoking Abstinence Questionnaire (SAQ):** Subject fills out form within REDCap Survey Queue. Verify form is completed before allowing participant to leave. Completed only at Baseline, Week 5, Week 6, Week 9, Week 13, and Month 1 Follow-up.
- **Symptoms/Side Effects Scale:** Subject fills out form within REDCap Survey Queue. Verify form is completed before allowing participant to leave. Completed at all visits, except Month 1 Follow-up.
- **Treatment Expectations:** Subject fills out form within REDCap Survey Queue. Verify form is completed before allowing participant to leave. Completed at all visits.
- **Treatment Satisfaction Survey:** Subject fills out form within REDCap Survey Queue. Verify form is completed before allowing participant to leave. Completed only at Week 5, Week 13, and Month 1 Follow-up.
- **Credibility Expectancy Questionnaire (CEQ):** Subject fills out form within REDCap Survey Queue. Verify form is completed before allowing participant to leave. Completed only at Week 5, Week 13, and Month 1 Follow-up.
- **Minnesota Nicotine Withdrawal Scale 2:** Subject fills out form within REDCap Survey Queue. Verify form is completed before allowing participant to leave. Completed only at Week 1, Week 2, Week 3, Week 4, and Week 5.
- **Questionnaire of Smoking Urges-Short Form 2 (QSU):** Subject fills out form within REDCap Survey Queue. Verify form is completed before allowing participant to leave. Completed only at Week 1, Week 2, Week 3, Week 4, and Week 5.
- **Alliance Questionnaire:** Subject fills out form within REDCap Survey Queue. Verify form is completed before allowing participant to leave. Completed only at Week 5.

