Smoking Abstinence Questionnaire (SAQ⁶¹). The SAQ assesses a smoker's expectancies for the process of smoking cessation on 10 scales. The SAQ scales have demonstrated good reliability and robust relationships with tobacco dependence, motivation to quit and abstinence self-efficacy, and withdrawal. (5 min)
Abstinence-Related Motivational Engagement (ARME⁶²). This 16-item scale assesses motivational changes after a quit attempt

on a 0-7 Likert scale. (5 min)
Attitudes about Nicotine Replacement-12 scale (ANRT-12) ⁶³ . This 12-item scale assesses smoker's attitudes about NRT and measures two factors: advantages (e.g., NRT will help with withdrawal symptoms and cravings) and disadvantages of NRT (e.g., NRT is addictive, side effects, etc.). (5 min)
Fagerström Test for Nicotine Dependence (FTND) ⁶⁴ . The FTND is a 6-item self-report measure of nicotine dependence from the Fagerström Tolerance Questionnaire ⁶⁵ . The FTND has satisfactory internal consistency and high test-retest reliability. (5 min)
Brief Wisconsin Inventory of Smoking Dependence Motives (WISDM-37) ⁶⁶ . The Brief WISDM has 37 items that load onto 11 subscales. The psychometric properties of the reduced-item WISDM subscales is comparable to the WISDM-68. (10 min)
Questionnaire of Smoking Urges-Brief Form (QSU) ⁶⁷ . The shortened version of the QSU assesses cravings associated with quitting smoking. The 10-item scale is scored on a Likert-style scale ranging from 1 (strongly disagree) to 7 (strongly agree). During Sessions 1-4, participants will complete this measure before and after their counseling sessions. (5 min)
Minnesota Nicotine Withdrawal Scale (MNWS) ⁶⁸ using DSM-IV criteria it assesses the physical and psychological symptoms associated with withdrawal. During Sessions 1-4, participants will complete this measure before and after their sessions. (5 min)
Treatment Satisfaction Survey (TSS) . This survey will be administered at the Product Selection session and subsequent sessions to determine satisfaction with both treatments. In addition to standard questions about different aspects of treatment (e.g., satisfaction with medication, satisfaction with therapy, etc.), participants will be queried about what aspects of the intervention they would change and how they would change it. (5 min).

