NRT Adherence	X	X	X	X	X	X	X	X	X	

Note: BL=Baseline Assessment; S=session; WK=week; M=month; PS=Product Selection; ¹All participants will complete these surveys twice (at the beginning and end of session) during sessions 1-4.

Randomization. We anticipate enrolling 10 pre-pilot participants in 3 months and 80 participants in 20 months and, based on our previous study with this population, expect to retain at least 70% through the one month follow-up point. Randomization will occur after completion of the initial screening and assessment.

Primary Outcomes. Feasibility and acceptability will be measured through high study retention (70%) and recruitment (recruitment of all participants within 24 months) in our groups. Additional items of acceptability include high scores on treatment satisfaction and credibility/expectancies that are equal or higher to the SC

group. Medication adherence is a third primary outcome with expected differences between our groups. Adherence is notoriously difficult to determine. Self-reported adherence is not always reliable, particularly during treatment studies where there is a demand characteristic to report the desired targeted behavior⁷³⁻⁷⁴ (e.g., adherence to NRT). The behavioral methods described under the assessment section represent the best available self-report tools for determining NRT adherence (e.g., TLFB report, returning used NRT patches and used product blister packs/packaging). Adherence will be defined by self-report using the TLFB and verified through returned patches and packaging. Good adherence is defined by taking greater than 80% of doses of medication at each time point. We have used these techniques in previous studies with low income populations with good compliance for use of TLFB verified by return of NRT materials⁷⁵.

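### At Week 5 the satisfaction and credibility forms are completed while the participant's own therapist checks the entries live, and the SAP does not name the time point for acceptability

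*Protocol*

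**What the plan says.** **Schedule.** The Protocol's Data Collection Parameters give the same rule for the TSS and the CEQ: "Completed only at Week 5, Week 13, and Month 1 Follow-up". SAP Table 2 marks the same three visits. SAP Table 1 says of the TSS: "This survey will be administered at the Product Selection session and subsequent sessions to determine satisfaction with both treatments". Product Selection is the Week 5 visit. The Protocol's Measurement Occurrence Chart adds Week 9 for both forms.

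**Week 5 visit.** Before counselling, the participant completes all session questionnaires in REDCap, "except the Alliance Questionnaire, SECOND Minnesota Nicotine Withdrawal Scale and the SECOND Questionnaire of Smoking Urges". While this goes on, staff are to "have REDCap open on the desktop and double check for participant entry errors as they progress through the questionnaires". These are steps 6 and 7 of the Week 5 list in Groups A to D, and steps 4 and 5 in the Control list.

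**Staffing.** The Therapy Protocol for Weeks 1 to 5 opens with: "Participants should work with the same staff member for the 5 weekly counseling sessions". The Week 5 list says of the Week 6 visit: "This appointment should be scheduled with another study staff member other than the therapist who saw the participant for the five weekly sessions". The Week 6, 9 and 13 lists repeat that rule for Week 9, Week 13 and the Month 1 Follow-up.

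**Use of the ratings.** SAP Primary Outcomes names satisfaction and credibility/expectancy as additional items of acceptability, alongside retention and recruitment. The criterion is high scores, no lower than in Standard of Care. The Aim 2 analysis compares the groups by t-test. Neither place gives a cut-off, a margin or a time point.

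**The concern.** Participants who know or suspect that their counsellor is reading a satisfaction or credibility form as they fill it in may answer more favourably. The TSS asks about satisfaction with the therapy, among other things. The counsellor at Week 5 has seen the participant in each of the four preceding weeks. If the ratings drift upward for that reason, the pilot can report high acceptability partly because of how the forms were collected. The criterion most exposed is the absolute one, high scores, because a shift common to both arms does not cancel there. The decision at stake is whether the intervention looks acceptable enough to carry into a full-scale trial.

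**Working it through.** No formula applies. The plan states no power, SD or margin for these ratings, so there is no figure of its own to reproduce. The check is a cross-reading of the two documents.

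1. **Are the forms due at Week 5?** Yes. The Measurement Occurrence Chart, Data Collection Parameters and SAP Table 2 agree on this visit.

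2. **Are they in the pre-session block?** Yes. The Week 5 lists hold back three forms: the Alliance Questionnaire, the second withdrawal scale and the second urges scale. The TSS and CEQ are not among them. By contrast, the Week 1 lists of Groups A to D do hold the CEQ back, and the Control lists for Weeks 1 to 4 place it after the session. Those entries do not match the CEQ schedule in step 1, but they do not alter the Week 5 instruction.

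3. **Is the block viewed live?** Yes. The checking step follows directly and makes no exception for any form.

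4. **By whom?** The step does not name the viewer. One staff member is to run all five weekly sessions, and the Week 5 list calls that person the therapist. The viewer is therefore in practice the participant's own therapist. This is an inference, but the text offers no other reading.

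5. **On how many occasions?**

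| Source | TSS/CEQ visits | With the therapist | With other staff |
|---|---|---|---|
| Data Collection Parameters; SAP Table 2 | Weeks 5, 13, Month 1 | 1 of 3 | 2 of 3 |
| Measurement Occurrence Chart | Weeks 5, 9, 13, Month 1 | 1 of 4 | 3 of 4 |

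Staff also check entries on the desktop at the later visits, but those staff are not the therapist.

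6. **Does Week 5 supply the acceptability result?** It may. The SAP names no occasion, so the Week 5 ratings are eligible and so are the others.

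7. **Is the effect the same in each arm?** The step is. Awareness of being read might not be. In Groups A to D the therapist graphs and discusses withdrawal and urge scores from Week 1. The Control lists first do so at Week 5, after the checked block. A differential effect is therefore conceivable, but nothing in the documents shows one.

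**The case against.** The strongest reply is that the safeguard already exists where it counts. The ratings at Week 13 and Month 1 are assigned to staff other than the therapist, and nothing says that Week 5 is the occasion that counts. That stands, and it confines the point to the Week 5 administration. A reader might infer that all the primary acceptability ratings are given in front of the therapist; the staffing rule contradicts this.

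Second, the purpose of the step is to catch entry errors, and no Week 5 step says that the participant sees the desktop or is told that answers are being read. The rule that staff be present while forms are completed is written for Baseline only. This also stands: the upward shift is plausible, not demonstrated. The check is not redundant either. The queue deals with omissions ("If a subject accidentally forgets to answer something, the survey prevents them from moving on"), not with wrong entries.

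Third, it is tempting to say that the SAP itself warns of this problem, since it writes that "there is a demand characteristic to report the desired targeted behavior". In context that sentence concerns self-reported medication adherence. The reasoning may carry over, but the SAP does not make the statement about satisfaction or credibility.

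Fourth, the CEQ rates the treatment, and the TSS rates several aspects of it, medication included. Neither is simply a rating of the therapist. The Alliance Questionnaire is not a listed primary outcome and is held back from the checked block, so it is not part of this point.

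Finally, acceptability does not rest on these forms alone, since the SAP also uses retention and recruitment. That limits the consequence but leaves the rating criterion exposed.

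**Conclusion.** The point holds for the Week 5 TSS and CEQ in all five groups. It is a modest weakness in data collection that is cheap to remove. It affects one of three scheduled administrations, or one of four by the chart. The likely direction is upward on the absolute ratings.

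The size in points cannot be derived. The documents give no score range, mean, SD or threshold for these ratings, and no evidence on how far answers shift when they are watched. Any figure would rest wholly on assumed inputs, so none is offered.

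A reader might go further and infer that a ceiling effect makes equality with Standard of Care easy to reach whatever participants think. The documents do not support that. The step is identical in every arm, and neither a ceiling nor an arm-specific shift is shown.

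The conclusion rests on two assumptions: that the same-staff rule is followed at Week 5, and that participants know or suspect that their answers can be seen.

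**What to change.** **Protocol.** In the five Week 5 lists (Groups A to D and Control), exempt the TSS and CEQ from the double-check step. The participant completes both on the tablet, unseen by the therapist, after being told that the therapist will not see the answers. For that statement to be true, the therapist should not open these two forms in the record. Checking of the other forms and entry of calendar data can go on as planned. Completion can still be verified, because the queue blocks skipped items and the Record Home Page marks finished surveys.

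**SAP.** Name the visit that supplies the acceptability result. If Week 5 is kept, the Protocol change protects it. The alternative is to name Week 13, where the ratings are already scheduled with non-therapist staff.

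**Cost.** One line in five lists and one sentence in the SAP. An occasional mis-keyed answer on these two forms will not be caught on the spot. Naming Week 13 would also mean rating after more dropout: with 80 randomised and the SAP's minimum expectation of 70% retained through the one-month follow-up, 80 × 0.70 = 56 participants would remain by that point.
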